1.1.4 Explorative objectives

Exploratory Objective:	Outcome Measure :
To compare the effect of dapagliflozin versus placebo on an expanded composite outcome reflecting worsening of HF.	Time to the first occurrence of any of the components of the expanded composite worsening HF outcome: 4. CV death 5. Hospitalization for HF 6. An urgent HF visit 7. Documented evidence of worsening HF symptoms/signs leading to initiation of a new treatment for HF sustained for at least 4 weeks or augmentation of existing oral therapy for HF (eg, increase in dose of diuretic) sustained for at least 4 weeks.
To determine whether dapagliflozin compared with placebo will have effect on New York Heart Association (NYHA) class.	Change in NYHA class from baseline.
To determine whether dapagliflozin compared with placebo will reduce the incidence of diagnosis of AF in patients without history of AF at baseline.	Proportion of patients without history of AF at baseline with a new diagnosis of AF during the study.
To determine whether dapagliflozin compared with placebo will result in a reduction of the incidence of hyper – and hypokalaemia.	Time to the first occurrence of each of any of the following central lab levels of serum potassium: 
 • >6.0 mmol/L • >5.5 mmol/L • <3.5 mmol/L • <3.0 mmol/L
To determine whether dapagliflozin compared with placebo will affect the number of events of doubling of serum creatinine.	Number of events with doubling of serum creatinine (compared with the most recent laboratory measurement).
To determine whether dapagliflozin compared with placebo will reduce the incidence of diagnosis of T2D in patients without diabetes at baseline.	Proportion of patients without T2D at baseline with a new diagnosis of T2D during the study.
To determine whether dapagliflozin compared with placebo will have effect on HbA1c in T2D subgroup.	Changes in HbA1c from baseline.

To determine whether dapagliflozin compared with placebo will have an effect on systolic BP.	Change in systolic BP from baseline.
To determine whether dapagliflozin compared with placebo will have an effect on body weight.	Change in body weight from baseline.
To determine whether dapagliflozin compared with placebo will reduce the incidence of myocardial infarction (MI).	Time to first fatal or non-fatal MI.

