4. ANALYSIS METHODS

4.1 General principles

No multiplicity adjustment will be made to confidence intervals as they will be interpreted descriptively and used as a measure of precision. All p-values will be unadjusted. P-values for variables not included in the confirmatory testing sequence, or following a non-significant test in the sequence will be regarded as nominal.

The primary and secondary analyses include adjudicated events occurring on or prior to PACD.

Stratification of analyses for T2D status will be performed using the stratification values as entered in IxRS to determine the randomization assignment.

Baseline diabetic status

T2D at baseline will be defined as established diagnosis of T2D (recorded in eCRF medical history) or central laboratory HbA1c $\geq 6.5\%$ at both visit 1 (enrollment) and visit 2 (randomisation).

Exploratory analyses may include “pre-diabetic” subjects not categorized as T2D above and having central laboratory HbA1c $\geq 5.7\%$ at visit 1 and/or visit 2. Other subjects will be categorized to a third group, here denoted “normo-glycaemic”

In consideration of missing data, subjects without medical history of T2D and a single HbA1c $\geq 5.7\%$ (including $\geq 6.5\%$) from visit 1 or visit 2 will be categorized as pre-diabetic. Subjects without medical history of T2D and no HbA1c measurement or a single measurement $< 5.7\%$ will be included in the normo-glycaemic group (thus non-diabetic).

Incomplete dates

All efforts should be made to obtain complete dates of clinical assessments and events. For analyses requiring complete dates, partially missing dates will be imputed based on available corroborating information. Absent of any additional corroborating information, partially missing dates will be imputed as follows: if only the year part of a date is available (YY), then the date will be set to YY0701. If only the year and month is available (YYMM), then the date will be set to YYMM15. Additional imputation rules will be defined as appropriate to ensure that eg, dates will not be imputed as prior to randomization, after death or end date before start date.

Baseline laboratory value

For all laboratory variables, with the exception of eGFR, the baseline value is defined as the last value on or prior to date of first dose of randomized study drug, or for patients who did not receive treatment, the last value on or prior to date of randomization.

eGFR

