4.2.3 Analysis of the primary efficacy variable

The primary variable is the time to first event included in the primary composite endpoint. The primary analysis will be based on the ITT principle using the FAS, including events with onset on or prior to PACD, adjudicated and confirmed by the CEA committee.

In the analysis of the primary composite endpoint, treatments (dapagliflozin versus placebo) will be compared using a Cox proportional hazards model with a factor for treatment group, stratified by T2D status at randomization, and adjusting for history of hospitalization for heart failure. The analysis will use WoC, non-CV death, last clinical event assessment and PACD for censoring of patients without any primary event as described in Section 3.1. The Efron method for ties and p-value based on the score statistic will be used. The event rates, p-value, HR, and 95% confidence interval will be reported.

The contribution of each component of the primary composite endpoint to the overall treatment effect will be examined. In the analysis of the components, all first event of the given type will be included irrespective of any preceding non-fatal composite event of a different type. Consequently, the sum of the number of patients with events in the component analysis will be larger than the number of patients with composite events. Methods similar to those described for the primary analysis will be used to separately analyze the time from randomization to the first occurrence of each component of the primary composite endpoint.

Kaplan-Meier estimates of the cumulative proportion of patients with event will be calculated and plotted, for the composite endpoint and for the individual components.

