4.2.4 Analysis of the secondary efficacy variables

The time-to-event secondary variables include

- time to the first occurrence of hospitalization for HF or CV death
- time to the first occurrence of any of the components of the renal composite endpoint
- time to death from any cause.

These endpoints will be analysed in the same manner as the primary variable, including stratification by T2D status at randomization. The composite of hospitalization for HF or CV death will be adjusted for history of hospitalization for heart failure. The renal composite endpoint will be adjusted for baseline eGFR. Censoring is described in Section 3.2 for each endpoint.

Additionally, exploratory subgroup analysis will be conducted for the secondary composite endpoint of CV death or HF hospitalization in the same way as the subgroup analysis for the primary endpoint.

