4.2.5.5 Laboratory Evaluation

All summaries of clinical chemistry/haematology parameters will be based on samples analyzed at the central laboratory, and presented in SI units.

The result and the change from baseline of each clinical chemistry/haematology tests, including estimated GFR, will be summarized by treatment group at each scheduled visit using descriptive statistics, including n, mean, SD, median and quartiles.

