4.2.6 Analysis of exploratory objectives

The analysis of the exploratory variables will in the same fashion as the primary and secondary efficacy variables be based on the ITT principle, including data irrespective of whether the patient has discontinued study drug.

The time to event endpoints including

- MI
- stroke
- first occurrences of serum potassium falling above/below defined thresholds
- the wider composite reflecting worsening HF (CV death, hospitalization for HF, urgent HF visit or worsening HF symptoms/signs leading to initiation of new treatment or augmentation of existing oral treatment)

will be analysed with the same methods as the primary endpoint.

Change from baseline to each visit for HbA1c, body weight, blood pressure and EQ-5D will be analysed with a repeated measures method. The analysis of HbA1c will be limited to patients with T2D at baseline as defined in Section 4.1. All non-missing visit data will be used, including measurements after discontinuation of study drug. The model will include terms for treatment group, visit, visit*treatment group and baseline measurement as a covariate. The model will be used to derive a least squares estimate of the treatment difference with 95% confidence interval and corresponding two-sided p-value. The missing data will not be imputed.

The proportion of patients with no worsening NYHA classification will be analyzed by a logistic regression by visit with treatment group, baseline NYHA and T2D at randomization. The odds ratio between treatment groups and its 95% confidence interval and corresponding two-sided p-value will be presented.

The proportion of patients with new diagnosis of T2D in non-diabetic patients (as defined in Section 4.1) will be analyzed by a logistic regression with treatment group and baseline HbA1c. The odds ratio between treatment groups and its 95% confidence interval and corresponding two-sided p-value will be presented. In addition to analysing patients who are non-diabetic at baseline, the subgroup of pre-diabetic patients as defined in Section 4.1 will be analysed.

The proportion of patients with new diagnosis of AF in patients without history of AF at baseline will be analysed with logistic regression with treatment group and T2D at randomization.

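### Time to hyper- and hypokalaemia is analysed without adjusting for baseline serum potassium, which gives up some power at the commoner thresholds

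*SAP*

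**What the plan says.** Section 1.1.4 defines the outcome as "Time to the first occurrence of each of any of the following central lab levels of serum potassium", with four cut-offs: above 6.0, above 5.5, below 3.5 and below 3.0 mmol/L. Section 4.2.6 lists these as "first occurrences of serum potassium falling above/below defined thresholds", groups them with MI, stroke and the wider worsening-HF composite, and says that all of them "will be analysed with the same methods as the primary endpoint". Section 4.2.3 gives that model: Cox regression with a treatment factor, "stratified by T2D status at randomization, and adjusting for history of hospitalization for heart failure". No section adds a potassium term.

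The baseline value exists. Section 4.1 states: "For all laboratory variables, with the exception of eGFR, the baseline value is defined as the last value on or prior to" first dose (or randomization, for untreated patients). Section 4.2.5.5 summarises change from baseline for every chemistry test, and potassium is among the chemistry variables in Appendix A, Table 2.

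Elsewhere the SAP does adjust for the baseline of what is being measured:

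- Section 4.2.4: "The renal composite endpoint will be adjusted for baseline eGFR".
- Section 4.2.4.2: the KCCQ responder regressions include baseline TSS.
- Section 4.2.6: baseline HbA1c for new T2D, baseline NYHA class for NYHA worsening, and the baseline measurement in the repeated-measures models.

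**The concern.** MI, stroke and the HF composite have no baseline value of the outcome to adjust for, so the primary model suits them. Potassium differs: the event is a later value of a laboratory variable crossing a fixed limit, and the starting value of that same variable is known. A patient who starts near the limit is more likely to cross it. Baseline potassium is therefore plausibly a stronger predictor than prior HF hospitalization, which is the covariate the model does carry.

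Leaving a strong predictor out of a Cox model lowers the power of the treatment test and moves the estimated hazard ratio (HR) towards 1. At stake is how much the trial can learn on its stated question of whether dapagliflozin reduces hyper- and hypokalaemia. That applies mainly at the two less extreme cut-offs, where there may be enough events.

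**Working it through.** **Inputs from the SAP.** Section 1.4 gives 4500 patients, 1:1 allocation, about 24 months' average follow-up, and primary sizing at HR 0.80, one-sided alpha 0.025, 844 events and 90% power. It gives no potassium mean, SD, incidence, sampling schedule, within-patient correlation or expected effect. Every potassium input below is an assumption.

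**Step 1: reproduce the plan's figure.** Schoenfeld, 1:1: events = 4(1.960 + 1.2816)² / (ln 0.80)² = 4 × 10.507 / 0.04979 = 844.1, or 845 rounded up. Power at 844 events is 0.900. The stated figure holds. It concerns the primary endpoint only.

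**Step 2: what the event count alone allows.** Take an assumed HR of 0.80 and power = Φ(√(events/4) × 0.2231 − 1.960).

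- About 406 events (placebo incidence 10%): Φ(2.248 − 1.960) = Φ(0.288) ≈ 61%.
- About 41 events (placebo incidence 1%): Φ(0.714 − 1.960) = Φ(−1.246) ≈ 11%.

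At the rare cut-offs a covariate has little power to recover.

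**Step 3: proportional-hazards simulation.** 4500 patients, conditional treatment HR 0.80, 400 trials per cell, one-sided 0.025. Baseline potassium has a log-HR of 0.5, 1.0 or 1.5 per SD. T2D strata and HF history are left out of both fitted models. The table shows power without → with baseline potassium, in %:

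| Placebo incidence | log-HR 0.5 | log-HR 1.0 | log-HR 1.5 |
|---|---|---|---|
| 1% | 10.0 → 10.2 | 9.0 → 8.7 | 6.8 → 6.8 |
| 3% | 23.7 → 22.0 | 19.8 → 19.3 | 19.3 → 20.7 |
| 10% | 61.5 → 64.5 | 57.3 → 64.0 | 45.5 → 57.8 |
| 15% | 74.8 → 77.7 | 68.5 → 75.5 | 61.3 → 77.5 |

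At 10-15% incidence the gain is about 3, 7 and 12-16 points as baseline becomes more prognostic. At 1-3% there is none beyond simulation error. That error is at most √(0.5 × 0.5 / 400) = 2.5 points per power figure; paired differences are tighter.

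**Step 4: visit-based simulation.** Mean 4.5 and SD 0.5 mmol/L, eight visits over 24 months, treatment shift 0.03 mmol/L away from the limit, 400 trials, two-sided 0.05. Relative efficiency is (mean z unadjusted / mean z adjusted)².

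| Correlation | Cut-off | Placebo incidence | Power, % | Relative efficiency |
|---|---|---|---|---|
| 0.3 | >5.5 | 13.9% | 32.0 → 36.2 | 0.93 |
| 0.3 | <3.5 | 14.0% | 36.5 → 37.2 | 0.94 |
| 0.5 | >5.5 | 11.6% | 29.5 → 33.3 | 0.82 |
| 0.5 | <3.5 | 11.5% | 28.7 → 31.5 | 0.85 |
| 0.6 | >5.5 | 10.3% | 25.0 → 32.0 | 0.76 |
| 0.6 | <3.5 | 10.2% | 25.8 → 34.7 | 0.81 |

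The two cut-offs are mirror images in this model, so their gains can be averaged:

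- Correlation 0.3: (4.2 + 0.7)/2 ≈ 2.5 points.
- Correlation 0.5: (3.8 + 2.8)/2 = 3.3 points.
- Correlation 0.6: (7.0 + 8.9)/2 ≈ 8.0 points.

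For >6.0 and <3.0 (incidence about 1%, 34-42 events) power stays between 7% and 14% with or without the covariate.

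**Step 5: a second visit-based set-up.** Limit 2 SD from the mean, 4-8 samples, about 8-10% of patients with an event, unadjusted HR about 0.8, 300 replicates, all FAS patients at risk. Power rises from 66.9% to 69.3% (correlation 0.3), 55.5% to 62.0% (0.5) and 52.1% to 60.5% (0.6). At 0.5 the mean z moves from −2.10 to −2.27, and (2.27/2.10)² = 1.17, so about 17% more information. If patients already beyond the limit at baseline are excluded, the gains are about 2, 4 and 9 points. The point therefore holds under either at-risk set.

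**Step 6: effect on the HR.** In Step 3 at 10-15% incidence the unadjusted HR averages 0.80-0.84 against a conditional 0.80. In Step 4 at the commoner cut-offs the adjusted HR lies 0.004 to 0.016 below the unadjusted one.

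**The case against.** The case for leaving the text alone is a serious one. The model in Section 4.2.6 is complete, pre-specified and valid. The endpoints are exploratory and outside the testing hierarchy. Section 4.1 makes such p-values nominal and confidence intervals descriptive, and the only power claim is for the primary endpoint. The size of the gain rests wholly on assumed inputs. At two of the four cut-offs it is likely to be nil in practice. All of this stands, and it sets the priority low. It does not remove the case for using a value that is already collected and defined, at almost no cost.

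Three stronger readings are tempting, and the documents do not support them.

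- *The unadjusted analysis is biased or its error rate is wrong.* It is not. Hazard ratios are non-collapsible, so the two models estimate different quantities, one averaged over baseline potassium and one conditional on it. The type I error of the unadjusted test is not in question.
- *The SAP contradicts its own principle.* It states no rule that laboratory endpoints are adjusted for their own baseline. The renal composite is in the confirmatory sequence, and one of its components is itself a decline from baseline, whereas the potassium limits are absolute. The other adjustments show that the change would fit the plan's practice; they do not make the present text inconsistent.
- *Adjustment can only help.* At 3% incidence two of the three cells in Step 3 fall slightly (23.7 → 22.0 and 19.8 → 19.3). These differences are within simulation error, so the fair statement is no material loss.

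**Conclusion.** The point holds as an efficiency improvement to a stated model. Section 4.2.6, read with Section 4.2.3, omits baseline serum potassium from the Cox models for the four potassium thresholds. The test remains valid but is less efficient where events are reasonably common.

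With about 8-15% of patients having an event and a within-patient correlation of 0.3 to 0.6, adjustment adds about 2 to 9 points of power. If baseline is very strongly prognostic (log-HR 1.5 per SD), the gain is about 12 to 16 points at 10-15% incidence. At incidences of about 1-3% there is no material effect. These sizes depend on assumed incidence, correlation and treatment effect, none of which the SAP supplies; the direction at the commoner thresholds is the same in all three simulations. No confirmatory conclusion is affected.

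**What to change.** In Section 4.2.6, take the potassium endpoints out of the general reference to the primary model. State that the Cox models for first serum potassium beyond each threshold are stratified by T2D status at randomization and adjusted for prior HF hospitalization and, in addition, for continuous baseline serum potassium as defined in Section 4.1. Missing baseline values are set to the mean of the patient's T2D stratum. Add that the resulting HR is conditional on baseline potassium and will usually lie slightly further from 1 than an unadjusted one.

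The cost is a sentence or two in the SAP and one covariate in existing code, with no new data. It should be settled before unblinding, because a covariate added afterwards would look data-driven.

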1.3.1 Randomization

Patients will be randomized 1:1 to either dapagliflozin 10 mg or placebo. Randomization will be stratified by type 2 diabetes (T2D) status at randomization (2 levels: with T2D; without T2D). T2D for stratified randomization is defined as established diagnosis of T2D or HbA1c more or equal to 6.5% (48 mmol/mol) shown at central laboratory test at enrolment (visit 1). See section 4.1 for definition of baseline diabetic status for analysis.

Randomization will be performed in balanced blocks of fixed size. The randomization codes will be computer generated and loaded into the IxRS (Interactive Voice/Web Response System) database.

The number of randomized patients with and without T2D will be monitored in order to ensure a minimum of 30% in each sub-population. Randomization may be capped (ie, no more patients can be randomized in a specific sub-population) if the pre-determined limit is reached.

Randomization of patients based on geographic region will be monitored to ensure global representation. LVEF category, NYHA class and atrial fibrillation status may be capped in IxRS to avoid over- or under-representation of these patient subgroups.

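### The repeated-measures model for body weight, blood pressure and EQ-5D leaves out T2D status at randomisation, the factor the trial was stratified on

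*SAP*

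**What the plan says.** Section 4.2.6 of the SAP puts four outcomes under one model: "Change from baseline to each visit for HbA1c, body weight, blood pressure and EQ-5D will be analysed with a repeated measures method". The terms are then listed: "The model will include terms for treatment group, visit, visit*treatment group and baseline measurement as a covariate". For one of the four the population is restricted: "The analysis of HbA1c will be limited to patients with T2D at baseline as defined in Section 4.1". No restriction by diabetes status is stated for body weight, blood pressure or EQ-5D.

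On the design, section 1.3.1 states: "Randomization will be stratified by type 2 diabetes (T2D) status at randomization". It adds that the numbers with and without T2D are "monitored in order to ensure a minimum of 30% in each sub-population".

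T2D at randomisation is carried into the primary Cox model (4.2.3), the secondary time-to-event analyses (4.2.4), and the KCCQ rank analysis and responder models (4.2.4.2). In section 4.2.6 itself, NYHA class is analysed by "logistic regression by visit with treatment group, baseline NYHA and T2D at randomization", and the new-AF model also has T2D at randomisation.

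**The concern.** A factor used to stratify randomisation is normally kept in the analysis model. Blocking within stratum removes chance imbalance in T2D between the arms. If T2D also predicts the outcome, a model without it leaves the between-stratum variance in the residual, and the reported standard error is larger than the sampling variation of the estimate. T2D can plausibly affect the course of weight and blood pressure.

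The SAP follows this practice almost everywhere else. In section 4.2.6 the models without T2D are the repeated-measures model and the new-onset T2D model, and the latter is limited to non-diabetic patients, so its omission explains itself. HbA1c has a matching reason. The other three outcomes have none. At stake is a little precision on exploratory outcomes, and consistency between neighbouring models.

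**Working it through.** **What the SAP gives.** It states no SD, T2D effect, baseline correlation or precision target for these outcomes, so there is no planned figure to reproduce. Its sample-size figures concern the primary endpoint only and do not bear on this point.

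**Does another section supply the missing term?** Section 4.1 says: "Stratification of analyses for T2D status will be performed using the stratification values as entered in IxRS". That fixes which T2D value to use when an analysis is stratified. It does not say that every analysis is stratified, so the list in 4.2.6 stands as written.

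**Inputs.**
- Share of patients with T2D, *p*: between 0.30 and 0.70, from the 30% minimum in 1.3.1. Hence *p*(1−*p*) lies between 0.21 and 0.25.
- T2D difference in change at a visit, given baseline, in residual SDs, *d*: assumed, from 0 to 0.5. A T2D difference in the baseline value itself does not count, because baseline is already a covariate.

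**Formula.** With the stratum in the model the residual variance is σ². With it left out, the variance is σ² + *p*(1−*p*)(*d*σ)². The ratio of interval widths, omitted to included, is therefore √(1 + *p*(1−*p*)*d*²).

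| *d* (assumed) | *p* = 0.30 or 0.70 | *p* = 0.50 |
|---|---|---|
| 0 | 1.000 | 1.000 |
| 0.1 | √1.0021 = 1.001 | √1.0025 = 1.001 |
| 0.2 | √1.0084 = 1.004 | √1.0100 = 1.005 |
| 0.3 | √1.0189 = 1.009 | √1.0225 = 1.011 |
| 0.5 | √1.0525 = 1.026 | √1.0625 = 1.031 |

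**Cross-check by simulation.** The set-up was 4500 patients, five visits, complete data, an unstructured covariance, 1:1 allocation within stratum and a T2D share of 0.45. The ratio of standard errors at the last visit (planned model over the model with the stratum added, same baseline slope at all visits) was 1.0000, 1.0014, 1.0057, 1.0098 and 1.0286 for *d* = 0, 0.1, 0.2, 0.3 and 0.5. This agrees with the formula.

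**Scale.** At *d* = 0.3 and *p* = 0.50 the variance ratio is 1.0225. If all 4500 patients contributed, the reported precision would match that of 4500/1.0225 ≈ 4401 patients, about 99 fewer.

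**The case against.** The strongest reply is that nothing is broken. The model is valid, section 4.1 does not require every analysis to be stratified, and the SAP chooses covariates endpoint by endpoint (baseline eGFR for the renal composite, for example). The outcomes are exploratory, their p-values are nominal, intervals are read descriptively, and any error is conservative. At *d* = 0.1 the widening is about 0.1%. All of this stands and keeps the point small. It does not explain why body weight, blood pressure and EQ-5D lack a term that NYHA class and new AF have, and adding it costs almost nothing.

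Two stronger readings are tempting, and the SAP supports neither.

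- A reader might infer that the intervals will certainly be wider than they should be. That needs T2D to predict change given baseline, which the SAP does not show. The loss can be zero.
- A reader might also count the missing baseline-by-visit term as an error, because a single baseline slope serves all visits in a study of about 33 months. If the slope at a visit departs from the common slope by *b*, and *k* is the baseline SD over the residual SD, the width ratio is √(1 + *b*²*k*²). For *b* from 0.1 to 0.2 and *k* from 1 to 2 this runs from √1.01 = 1.005 to √1.16 = 1.077, and it is exactly 1 if the slope is constant. These inputs are assumed throughout. Nothing in the SAP requires the term, and treatment-by-visit is already there to give visit-specific contrasts. It is a modelling option.

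**Conclusion.** The point holds as a minor inconsistency with a small possible loss of precision. The model for body weight, blood pressure and EQ-5D omits the randomisation stratum without a stated reason, while neighbouring models include it. The resulting intervals are between 0% and about 1% wider for T2D effects up to 0.3 residual SD, and about 3% wider at 0.5 SD.

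The size rests on assumed effect sizes, on a T2D share of 30% to 70%, on complete data, and on a T2D shift that is the same at every visit, so that a single term captures it. Stratified allocation keeps the arms balanced on T2D, so leaving it out does not bias the randomised contrast. No confirmatory test is affected.

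**What to change.** In section 4.2.6, add T2D status at randomisation, using the IxRS value as in section 4.1, to the listed terms for body weight, blood pressure and EQ-5D. State that the term is left out for HbA1c because that analysis is limited to patients with T2D at baseline. If the omission is deliberate for the other three outcomes, give the reason instead. A baseline-by-visit term may be added at the sponsor's discretion.

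The cost is one line in the SAP and one degree of freedom. No new data are needed, since the stratum is already recorded for every randomised patient.
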